## **8.0 RISKS – OTHER THAN THE STUDY DRUG**

**8.1 Psychological and Behavioral Assessment Risks:** At screening, subjects will undergo non-invasive

psychological assessment of a structured nature that has been consistently used without adverse effects in previous studies with a similar subject population. There is the potential risk that subjects may become fatigued during the performance of screening assessments or behavioral tasks, and that discussion of personal issues with study personnel in the context of screening issues may be stressful or uncomfortable. Because subjects participating in this study will be stable outpatients, it is unlikely that the stress posed by such measures will exacerbate baseline psychiatric symptoms.

**Minimizing the Risk of Psychological and Behavioral Assessment:** The risk of the diagnostic evaluation involves the possibility that participants may be asked questions which cause them distress. These would be questions consistent with any clinical evaluation. In order to address this risk, participants will be told they can decline to answer any questions and can stop the evaluation at any time.

### **8.2 MRI Scan Risk:**

1. Ferromagnetic objects brought into the room will be pulled toward the magnet.
2. Due to the magnetic properties of the scanner, if a subject has implanted metal or medical devices they may experience abnormal torques or failure to function properly. This may cause injury to the body areas where the device is located.
3. There is a risk of tissue heating if there is excessive power deposition of radiofrequency (RF) magnetic waves. Excessive RF waves emitted could cause the atoms to transmit high-frequency RF wave at such a rate as to cause the neighboring tissue to heat.
4. There is a risk of peripheral nerve stimulation if gradients are switched too rapidly. Switching a gradient will increase the magnetic field strength in specific area. This in turn, increases the current in that area. If the field strength is switched too rapidly, the amount of current will increase to the point of tissue excitation.
5. The subjects may experience a claustrophobic reaction in the magnet.
6. There are loud banging noises with MR imaging that may be uncomfortable.

### **Regarding the MRI procedures we will employ the following protections:**

1. The subject will be instructed not to bring metal objects into the magnet room and will be provided with lockable facilities for personal belongings.
2. The use of the MRI screening form will exclude from the study potential subjects with implanted metal or medical devices.
3. The FDA has strict limits regarding power deposition. Safeguards built into the operating system prevent exceeding those limits.
4. The FDA has strict limits regarding gradients strengths and rise times. Safeguards built into the operating system prevent exceeding those limits.
5. Subjects will be warned of the potential for claustrophobic reactions and those with a prior history of such reactions will be excluded from the study. If a subject experiences an unexpected and severe claustrophobic reaction, the study will be terminated.
6. Subjects will be provided with hearing protection.

**Potential Risks to Subjects (Rare/Unforeseen):** There have been no appropriate studies that either rule out or demonstrate negative health effects of MRI on fetuses. We will inform women with child-bearing potential of this information and pregnant women will not be allowed to participate. If new information becomes available to suggest that MRI may not be safe for pregnant women or their fetuses we will inform the subjects of such information.

**8.3 Blood draw risk:** Commonly, there may be discomfort or pain at the site at the time of venipuncture, or bleeding or bruising post-venipuncture. Uncommonly, there is a very small risk of infection, which can be treated. Participants will be asked to contact their PCP and the study PI in the event of any adverse outcome.

**8.4 Minimizing risk of Breach of Data Security and Privacy:** Data obtained from human subjects will be

confidential and accessed only by members of the study team with appropriate IRB and HIPAA training, as assured by standard training protocols at VUMC. Data is maintained and secured in locked file cabinets or on encrypted, password protected computers, located in locked offices, and following Health Insurance Portability and Accountability Act (HIPAA) guidelines and the policies and procedures of VU and VUMC. Individuals will be identified by a numerical code that will be kept separate from study data.

## **9.0 REPORTING OF ADVERSE EVENTS OR UNANTICIPATED PROBLEMS INVOLVING RISK TO PARTICIPANTS OR OTHERS**

---

We define an adverse event as any adverse change in health or development of a side effect occurring in a study participant after enrollment. These may be expected events (known drug effects, as detailed in the consent form, safety monitoring plan, or package insert) or unexpected events. The PI and Co-investigators will review any AE's that occurred during a participant's study experience, and determine their magnitude and causal attribution using the scale below. Every six months the PI and Co-investigators will review the magnitude and frequency of AE's and report such information to the IRB.

AE's of grade three or higher in the scale below will be reported immediately to the IRB using the Report of Adverse Events form and to the Program Director of the appropriate funding agency. In conjunction with the IRB, the PI then will determine if modifications to the protocol are warranted.

The primary method for ensuring data accuracy and protocol compliance will be the involvement of the PI in all aspects of the project. The PI and IRB have the authority to stop or modify the study at any time. During the semi-annual reviews, the PI and IRB will together decide if the study should continue unchanged, be modified, or closed to further enrollment.

### Scaling of Adverse Events: Attribution of Cause:

- a. Definite: Adverse event (AE) will clearly be related to investigational agents or other intervention.
- b. Probable: AE will likely be related to investigational agents or other intervention.
- c. Possible: AE may be related to investigational agents or other intervention.
- d. Not Likely: AE will doubtfully be related to investigational agents or other intervention.
- e. Unrelated: AE will clearly not be related to investigational agents or other intervention.

### Grading of Severity

0: No AE or within normal limits.

1: Mild AE.

2: Moderate AE.

3: Severe AE resulting in inpatient hospitalization, a persistent or significant disability/incapacity, or a congenital anomaly/birth defect.

4: Life-threatening or disabling AE.

5: Fatal AE

## **10.0 STUDY WITHDRAWAL/DISCONTINUATION**

---

Subjects will be withdrawn from the study for safety considerations, non-compliance with study procedures, difficulties with scheduling or participation, excess movement or anxiety during scanning, or other reasons that the PI or study coordinators conclude will impair the scientific utility of the study. Subjects will be provided an explanation by the investigator if they are withdrawn from the study. In addition, subjects can voluntarily withdraw from the study at any time.

## **11.0 STATISTICAL CONSIDERATIONS**

---

**11.1 Data Management:** All study data will be stored in a REDCap study database. The exception is for the raw and processed MRI scans that will be stored in the Vanderbilt XNAT Image Database system.

## 11.2 Statistical Analyses:

**11.2.a. Drug levels:** We will collect serum drug levels at the time of imaging to create a dose-response curve. The response will be defined as the change of a specific measure (hippocampal activity) from baseline. We will utilize nonlinear regression methods to create curves. Many studies have established a dose-response curve for epilepsy efficacy and safety (Boon et al., 2002; Meencke and Buyle, 2006; Rhee et al., 2017), but no dose-response curve currently exists for other measures such as imaging markers.

**11.2.b. Clinical Data:** The data will be analyzed both within and across diagnostic groups (patient, healthy control) and time-points (baseline assessment, after LEV intervention). Analyses of variance and linear mixed models will be used to compare group scores and the strength of the relation between neurocognitive and imaging outcome measures.

**11.2.c. Neurocognitive Data:** The data will be analyzed both within and across diagnostic groups (patient, healthy control) and time-points (baseline assessment, after LEV intervention). Analyses of variance and linear mixed models will be used to compare group scores.

**11.2.d. Imaging Data:** All images will be converted to an analyzable format. Spatial preprocessing will be performed using SPM5 (Functional Imaging Laboratory, London, UK) and FSL software (Analysis Group, FMRIB, Oxford, UK) or other comparable software. This will allow for realignment and transformation into a standardized space. Pairwise subtractions will then be performed, yielding images of mean difference and standard deviation, which can be used to produce z-scores and statistical parametric maps (SPMs). Statistical parametric maps will be constructed using a mixed effects model (subjects are considered random effects, conditions are considered fixed effects). SPM or other comparable software will allow us to test for condition effects, group effects, and group-by-condition interactions. Duration of illness and treatment will be assessed as confounding variables using an analysis of covariance. The duration of illness will be added into the fixed effects statistical model for the within group analysis as a covariate. Alternative methods will be employed when the data suggest a more appropriate method. The effects of duration of illness and treatment on structural imaging data will be assessed by correlation analysis.

**11.3 Power:** We calculated power for our primary aim of modulation of hippocampal activity based on a similar study that detected changes in hippocampal activation between healthy controls and a group of aMCI patients receiving two weeks of oral LEV (Bakker et al., 2012). Using the effect sizes demonstrated in this paper, at  $N = 40$  (healthy control sample  $N = 20$ ; psychosis patient sample  $N = 20$ ) and  $\alpha = 0.05$ , we will have 80.3% power to detect a change in hippocampal activity.

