**Primary Aim: To determine whether administration of oral LEV over two weeks modulates hippocampal hyperactivity**

Hypothesis 1: Oral LEV will decrease, in a dose-response relationship, hippocampal activity in healthy control subjects and psychotic patients (ASL study).

Hypothesis 2: Oral LEV will normalize hippocampal recruitment in patients (Scene-processing fMRI study).

Hypothesis 3: Compared with healthy control subjects, psychotic patients will show higher hippocampal activity (ASL study) and reduced hippocampal recruitment (Scene-processing fMRI study).

**Secondary Aim: To determine whether administration of oral LEV over two weeks improves clinical symptoms in patients with psychotic disorders**

Hypothesis 1: Oral LEV will improve cognitive symptoms in psychotic patients (eye-tracking relational memory task).

Hypothesis 2: Oral LEV will reduce positive and negative psychotic symptom severity (Positive and Negative Syndrome Scale, PANSS).

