**6.5 MRI Procedures:** MRI scans of the brain will be obtained using the MRI scanners in the Center for Human Studies in the Vanderbilt University Institute for Imaging Science (VUIIS), located in the Vanderbilt Hospital and Medical Center North. This will require approximately 60-90 minutes. There will be a total of three MRI scans in this study (baseline assessment, two hours after the initial LEV dose, and after two-week intervention of LEV).

**6.5.a MRI Screening:** The participant will fill out the MRI Procedure Screening Form. The purpose of this form is to ensure that there are no implanted medical devices or metals that could injure the subject if exposed to a high magnetic field. This form will be filled out in a private room adjacent to the MRI scanner and reviewed by the MR Technologist and the research assistant.

**6.5.b Scanning Procedures:** Imaging studies will take place on a Phillips 3.0 T MRI scanner. The magnet and the magnet's control console are in separate rooms, but the investigator and the subject will be in voice communication at all times, and the investigator will be able to see the subject through a window. All data acquired on the scanner will be securely transferred over the Vanderbilt network to the Institute of Imaging Science's server. Imaging data will be de-identified and only be accessible to the PI, co-investigators, and VUIIS personnel. Scanning procedures may include: 1) Structural imaging, 2) Resting state functional imaging, 3) ASL imaging to non-invasively measure cerebral blood flow, and 4) Functional imaging with task – while in the scanner, participants will view images that include faces,

objects and scenes. Images are projected to a mirror above the participants head from a projector located outside the scanner room. Some runs will repeat the same face or object, some runs will present different images. Participants will complete between 1-8 runs of this task. To maximize participant's attention to the images, participants will be instructed to push a button to detect targets. Targets may include image repeats or changes in the image (e.g., image size). This task is similar to the reported in McHugo et al., 2019.

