**6.6.b. Timing Rationale:** We selected a two-hour duration for the first imaging assessment based on LEV's absorption and clearance data. The pharmacokinetics will be reviewed in more detail in sections 7.2 and 7.3. Briefly, LEV is rapidly and almost completely absorbed after oral administration, with peak serum concentrations occurring approximately one hour after dose (Gambardella et al., 2008). Based on a study that measured LEV plasma concentrations ( $\mu\text{mol/L}$ ) over time after oral ingestion of varying doses of LEV (500-5000mg) in healthy volunteers, LEV levels will be approximately 9.75 mcg/mL (57.3  $\mu\text{mol/L}$ ) at two hours (Patsalos, 2004). Therefore, two hours after LEV administration is the earliest time-point where we can assess study participants at a sub-therapeutic epilepsy dose (10-40 mcg/mL) of LEV (Bakker et al., 2015, 2012; Lyseng-Williamson, 2011).

**6.6.c Duration Rationale:** We selected a 2-week duration because of other studies that have been able to safely demonstrate changes in cognitive performance and changes in hippocampal activation (Bakker et al., 2015, 2012) after 2 weeks of LEV intervention in patient cohorts outside the FDA-approved indications for LEV.

**6.6.d Compliance:** We will assess compliance using the Medication Adherence Questionnaire, a medication count after two weeks, and a test for LEV blood levels.

**6.6.e Concomitant medications:** We will allow concomitant use of any medication approved by the US FDA unless specified in our inclusion/exclusion criteria (e.g. normal controls using psychotropic medications). Reviews have indicated that LEV does not affect the metabolism of other drugs, including antipsychotics (Besag and Berry, 2006).

**6.7 Blood Draw:** Subjects will undergo three separate blood draws. The first blood draw will occur during the

Screening and Enrollment visit. The second blood draw will occur during the short-term intervention assessment. The third blood draw will occur during the long-term intervention assessment. Both visits will use blood draws to assess GFR and CBC, as addressed in the study drug risks below. During the short-term intervention visit, we will check LEV levels for the study of a dose-response relationship with blood flow. During the long-term intervention visit, participants will undergo a blood draw to check LEV levels to ensure compliance with taking the study medication.

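### Section 11.2.a analyses raw change from baseline against serum level without a baseline covariate, which gives up precision, and it does not name the scan that enters the curve

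*Combined protocol and SAP*

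**What the plan says.** Primary Aim Hypothesis 1 in section 2.0 reads: "Oral LEV will decrease, in a dose-response relationship, hippocampal activity in healthy control subjects and psychotic patients (ASL study". The analysis meant to address the dose-response part is section 11.2.a, Drug levels. It says "We will collect serum drug levels at the time of imaging to create a dose-response curve", then "The response will be defined as the change of a specific measure (hippocampal activity) from baseline", then "We will utilize nonlinear regression methods to create curves". It gives no functional form, covariate, subject effect or error structure.

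Section 6.5 says "There will be a total of three MRI scans in this study": at baseline, two hours after the first dose, and after two weeks. So two scans per person are taken on LEV. Section 6.7 gives the two on-drug levels different purposes. For the first: "During the short-term intervention visit, we will check LEV levels for the study of a dose-response relationship with blood flow". For the second: "participants will undergo a blood draw to check LEV levels to ensure compliance with taking the study medication".

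Elsewhere in section 11.2, linear mixed models are named for the clinical and neurocognitive data, and the parametric maps in 11.2.d use a mixed model ("subjects are considered random effects, conditions are considered fixed effects"). The only covariates named are duration of illness and treatment, both in 11.2.d. Baseline hippocampal activity is not named as a covariate anywhere.

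**The concern.** When the response is on-drug value minus baseline value, the measurement noise of the baseline scan passes in full into the residual of the level-response fit. Baseline is measured before any drug is taken and is planned for everyone, so it can serve as a covariate. The fit then chooses how much weight baseline gets instead of fixing that weight at one.

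Precision is scarce in this analysis. Section 6.6 gives everyone the same first dose, and section 7.2 describes levels as varying little between people. The curve must therefore be drawn from a narrow spread of levels in a sample that section 5.3 hopes will reach at least 20 controls and 20 patients. A slope less precise than the data allow makes a true level-response relation easier to miss.

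**Working it through.** **The plan's own figure.** Section 11.3 states 80.3% power at N = 40 and α = 0.05 for a change in hippocampal activity. It gives no effect size, SD, test or sidedness, so the figure cannot be reproduced. It is not a power for the serum-level regression, which has none, and nothing below depends on it.

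**Inputs.** n = 40 (20 + 20, section 5.3), and n = 20 for one group alone. The test-retest correlation ρ is not in the documents; values from 0.3 to 0.9 are assumed. Further assumptions are equal variance s² at both scans, one on-LEV scan per person, a linear slope, and level unrelated to baseline.

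**Residual variance.**
- Raw change: 2s²(1 − ρ).
- With baseline as covariate: s²(1 − ρ²).
- Ratio: (1 − ρ²) / [2(1 − ρ)] = (1 + ρ)/2.

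The adjusted model subtracts about ρ times baseline instead of one times baseline. Baseline noise therefore counts for less, but it is not removed: 1 − ρ² stays above zero for any ρ below 1.

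**Slope variance in a finite sample.** With one normally distributed regressor, the slope variance is proportional to 1/(n − 3). Adding one covariate makes it 1/(n − 4). The ratio is multiplied by 37/36 at n = 40 and by 17/16 at n = 20.

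| ρ (assumed) | (1 + ρ)/2 | n = 40 (× 37/36) | cut in variance | n = 20 (× 17/16) | cut in variance |
|---|---|---|---|---|---|
| 0.3 | 0.65 | 0.668 | 33% | 0.691 | 31% |
| 0.5 | 0.75 | 0.771 | 23% | 0.797 | 20% |
| 0.7 | 0.85 | 0.874 | 13% | 0.903 | 10% |
| 0.8 | 0.90 | 0.925 | 8% | 0.956 | 4% |
| 0.9 | 0.95 | 0.976 | 2% | 1.009 | none |

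Simulation of the linear slope (8,000 runs per setting) at ρ = 0.3, 0.5, 0.7 and 0.9 gave ratios of 0.654, 0.776, 0.883 and 0.975 at n = 40, and 0.695, 0.791, 0.899 and 1.005 at n = 20. These agree with the formula to within about 0.01.

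On the standard-error scale the n = 40 gains are smaller: √0.668 = 0.817, √0.771 = 0.878, √0.874 = 0.935, √0.925 = 0.962 and √0.976 = 0.988. These are cuts of about 18%, 12%, 7%, 4% and 1%.

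**If both on-LEV scans were pooled.** Let r01, r02 and r12 be the correlations between the baseline, two-hour and two-week scans. With equal variances, a person's two changes correlate q = (1 − r01 − r02 + r12) / [2√((1 − r01)(1 − r02))]. This equals 0.5 when all three correlations are equal, and ran from 0.17 to 0.70 over the patterns tried. If rx is the correlation of the person's two serum levels, the ratio of naive to true standard error of the slope is 1/√(1 + rx·q). At q = 0.5:

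| rx (assumed) | naive/true SE | simulated type I error, n = 40, nominal 5% |
|---|---|---|
| −0.5 | 1.15 | 2.5% |
| 0 | 1.00 | 4.8% |
| 0.5 | 0.89 | 8.1% |
| 0.9 | 0.83 | 10.8% |

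The error can go either way. Baseline adjustment alone does not cure it: with equal correlations the two adjusted residuals still correlate ρ/(1 + ρ), for example 0.5/1.5 = 0.33 at ρ = 0.5.

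**The case against.** **Change from baseline is a legitimate response.** It is natural for a concentration-effect curve, since no drug should mean no drug-related change. This stands: the plan's analysis is inefficient, not invalid. It also stands that the gain rests on an undocumented ρ, vanishes near 0.9, and was worked out for a linear slope whereas the plan names nonlinear regression.

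**Serum level is not randomised.** If level is related to baseline activity, the change slope and the adjusted slope can differ, so the swap would not be a pure precision gain. That is true, but it does not favour raw change. Suppose level has no effect, correlates −0.3 with baseline, and ρ = 0.7. Raw change then shows a slope of 0.3 × (1 − 0.7) = 0.09 SD per SD of level, purely from regression to the mean, while the adjusted slope is about zero. The precision gain does shrink in that case: the variance ratio is [0.51/(1 − 0.09)] / (0.60 − 0.09²) × 37/36 = 0.97.

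**A stronger reading.** Because 11.2.a names no visit and there are two on-LEV scans, a reader might infer that two changes sharing one baseline will be fitted as independent, so that Hypothesis 1 gets p-values that are too small. The documents do not support this. Section 6.7 ties dose-response to the short-term level and gives compliance as the purpose of the long-term one, which points to one change per person. Nothing says that both enter one curve or would be treated as independent. Even if they did, the slope's standard error would be too small only if a person's two levels correlate positively. Section 7.2's description of time-invariant pharmacokinetics makes that plausible but does not establish it, and the two visits follow different regimens (section 6.6).

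**Conclusion.** The point holds as an optional, nearly free improvement. Section 11.2.a uses raw change with no baseline covariate and so discards some precision on the level-response slope of Hypothesis 1. For assumed test-retest correlations of 0.3 to 0.8, the avoidable share of the slope's variance at n = 40 runs from about 33% down to 8%. At 0.9 it is 2 to 3%, and nil with 20 people. This rests on equal variances, a linear slope, one on-LEV scan per person, and level unrelated to baseline.

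Separately, 11.2.a does not say which scan enters the curve, and it should be reconciled with 6.7. No inflated type I error can be claimed from the text as it stands.

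**What to change.** In section 11.2.a:

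1. Name the on-LEV scan and level that enter the curve, in agreement with section 6.7.
2. Model the on-LEV hippocampal value as a function of serum level, with the person's baseline value and group as additive covariates. Keeping change as the response and adding the same covariates gives the same level coefficient in a linear model, so the present definition of response could also stay.
3. State that this adjustment is for the level-response slope only. It should not carry over to the patient-control comparison of change, because Hypothesis 3 expects the groups to differ at baseline and adjusting would change what that comparison estimates.
4. If both on-LEV scans are to be pooled, say so and add a per-person random effect in addition to the baseline covariate.

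The cost is a few sentences and one or two degrees of freedom. No extra scan, blood draw or participant is needed.

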### **Inclusion criteria for psychosis subjects**

1. Men and women age 18 - 65.
2. Communicative in English.
3. Provide voluntary, written informed consent.
4. Physically healthy by medical history.
5. BMI > 17.5 and < 45.
6. Diagnosis of a psychotic disorder confirmed by Structured Clinical Interview for DSM-V (SCID) or diagnostic interview with a trained clinician.
7. Stable medication regimen over at least the past two weeks, including the use of either an oral or intramuscular administration of an antipsychotic medication.
8. For females, no longer of child-bearing potential, or agreeing to practice effective contraception during the study (e.g., established use of oral, injected or implanted hormonal methods of contraception; placement of an intrauterine device [IUD] or intrauterine system [IUS]; barrier methods: condom with spermicidal foam/gel/film/cream/suppository or occlusive cap [diaphragm or cervical/vault caps] with spermicidal foam/gel/film/cream/suppository; male partner sterilization; or true abstinence when this is in line with the preferred and usual lifestyle of the subject); and,
9. For females of child-bearing potential, must have negative urine pregnancy test at time of screening visit and before each testing day.
10. Not breastfeeding/nursing at time of screening or at any time during the study.

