**5.1.c Greater Nashville Area:** Individuals who may meet criteria for one of the proposed study diagnoses (as determined by self-identification) and healthy non-psychiatric control subjects will be recruited through mass email ads through the Vanderbilt University Medical Center email system, study advertisements distributed/posted in the community, Vanderbilt General Clinical Research normal volunteer program, the Vanderbilt Kennedy Center, and mass email ads through the Vanderbilt University Medical Center email system. If potential subjects are interested in participating in this study and appear to meet inclusion and exclusion criteria (based on initial screening), a meeting with the RA will be scheduled. At this meeting, the informed consent form will be reviewed with the subject. The subject will be encouraged to carefully read the consent form and ask questions. If the subject appears to meet inclusion and exclusion criteria and wishes to participate in this study, informed consent will be obtained, and Study Procedures will be performed.

**5.2 Monetary Compensation:** All study subjects will be remunerated \$25 for completion of the screening and consent visit, regardless of their decision to enroll in the study or their eligibility to enroll. Because of the study design, subjects only yield meaningful primary outcome data if they complete the long-term intervention phase session. They will therefore be compensated an additional \$475 at the completion of the remaining study visits. This incentivization is designed to yield greater benefit from the research, thereby improving the risk/benefit ratio of the study.

**5.3 Recruitment:** We will make every effort to recruit equal numbers of men and women. We will not exclude subjects based on gender or minority status. We minimize coercion throughout the study by repeatedly informing subjects that they may discontinue study procedures at any point, or opt-out of any specific part of the study they become uncomfortable with completing.

We plan to recruit up to 60 subjects (up to 30 healthy control subjects and up to 30 patients with psychotic disorders) for the study. We hope to acquire analyzable data from at least 20 control subjects and 20 patients.

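### The structural-imaging correlation with illness duration names no age adjustment in patients aged 18 to 65, so an association could partly or wholly reflect ageing

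*Combined protocol and SAP*

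**What the plan says.** The last sentence of section 11.2.d (Imaging Data) reads: "The effects of duration of illness and treatment on structural imaging data will be assessed by correlation analysis". It names no structural measure, covariate or significance level.

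Where the same paragraph wants covariates elsewhere, it names them: "Duration of illness and treatment will be assessed as confounding variables using an analysis of covariance", and "The duration of illness will be added into the fixed effects statistical model for the within group analysis as a covariate". Age is in neither list. Just before the structural sentence there is an open clause: "Alternative methods will be employed when the data suggest a more appropriate method".

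The first inclusion criterion for patients in section 4.0 is "Men and women age 18 - 65". Section 5.3 plans "up to 30 healthy control subjects and up to 30 patients with psychotic disorders" and adds: "We hope to acquire analyzable data from at least 20 control subjects and 20 patients". Section 6.5.b makes the structural scan optional: "Scanning procedures may include: 1) Structural imaging, 2) Resting state functional imaging". No aim or hypothesis in section 2.0 uses a structural outcome.

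**The concern.** For each patient, duration of illness equals age minus age at onset. Over an age span of 47 years (65 - 18), duration must track age closely unless age at onset varies about as widely as age itself. If the structural measure also changes with age, a correlation with duration that ignores age has a non-zero expected value even when duration has no influence of its own. The plan would describe the result as an effect of illness duration.

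A larger sample does not help. The bias stays the same while the standard error shrinks, so a spurious result becomes more likely. What is at stake is the reading of one ancillary result: a reader could not tell illness progression from ordinary ageing.

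**Working it through.** **The plan's own figures.** The plan gives none for this analysis. The 80.3% power in section 11.3 concerns hippocampal activity under the primary aim and has no bearing here.

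**Inputs from the documents.** Patient age 18 to 65 (section 4.0); at least 20 patients with analyzable data hoped for, 30 at most (section 5.3).

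**Inputs assumed.** The documents give neither r(age, duration) nor r(age, structure). The test is taken as two-sided at 5%; section 11.3 states alpha 0.05 only for the primary aim. The check covers illness duration, not treatment.

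**Step 1: plausible age-duration correlation.** With age uniform over 18 to 65 and onset averaging 23 years, simulation gives r = 0.95, 0.90, 0.85 and 0.80 for onset SDs of 4, 6, 8 and 10 years. If recruits were in practice aged 18 to 35 with mean onset 21, r = 0.69 (SD 4) and 0.56 (SD 6).

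**Step 2: expected correlation with no true duration effect.**

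r(duration, structure) = r(age, duration) × r(age, structure)

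Assumed central case: 0.8 × (-0.3) = -0.24.

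**Step 3: false-positive rate in the central case.** Simulation with 40,000 runs gives 17.5% at n = 20 and 24.9% at n = 30. A Fisher-z check, with atanh(0.24) = 0.245:

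- n = 20: 0.245 × √17 = 1.01. P(Z > 1.96 - 1.01) is about 17%.
- n = 30: 0.245 × √27 = 1.27. P(Z > 1.96 - 1.27) is about 25%.

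**Step 4: sensitivity** (40,000 runs per cell, no true duration effect, no age adjustment).

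| r(age, duration) | r(age, structure) | Expected r | n = 20 | n = 30 |
|---|---|---|---|---|
| 0 | any tested | 0 | 5% | 5% |
| 0.5 | -0.2 | -0.10 | 7% | 8% |
| 0.5 | -0.4 | -0.20 | 13% | 19% |
| 0.7 | -0.2 | -0.14 | 9% | 11% |
| 0.7 | -0.4 | -0.28 | 23% | 33% |
| 0.9 | -0.2 | -0.18 | 12% | 16% |
| 0.9 | -0.4 | -0.36 | 35% | 51% |
| 0.9 | -0.6 | -0.54 | 73% | 89% |

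**Step 5: after adjustment.** The partial correlation given age rejected in 4.7% to 5.2% of runs in every setting tested, at both sample sizes.

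**Step 6: price of adjustment.** Variance inflation is 1 / (1 - r²), with r the age-duration correlation.

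- r = 0.8: 1 / (1 - 0.64) = 2.8, so the standard error is about √2.8 = 1.7 times larger.
- r = 0.95: 1 / (1 - 0.9025) = 10.3, so about 3.2 times larger.

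**The case against.** The strongest reply is that the plan does not say age will be left out. A correlation analysis can be a partial correlation, and the alternative-methods clause leaves room for one. A reader might infer a deliberate decision to ignore age, and the text does not show that. But neither wording commits to age, and the paragraph does name covariates where it wants them. The link between age and duration also follows from the definition of duration, so it can be handled in advance instead of waiting for the data to suggest a method.

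Second, the size rests on assumed correlations. This stands. An eligibility range of 18 to 65 does not fix the ages recruited, and a younger sample with a measure only weakly related to age brings the rate close to nominal. The 5% benchmark is also an assumption for this analysis.

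Third, the analysis is peripheral. This stands too: the scan is optional, no structural measure is named, and the aims rest on ASL, task fMRI, eye-tracking and PANSS.

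Fourth, adjustment may leave the question unanswerable with 20 to 30 patients. That is true. But a wide adjusted interval shows the limitation, whereas the unadjusted correlation conceals it.

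**Conclusion.** The point holds as a minor but concrete weakness in the choice of analysis. Followed as written, section 11.2.d mixes ageing with illness duration. Under the assumed correlations of 0.8 and -0.3, the false-positive rate is about 18% with 20 patients and 25% with 30, against 5%. It is 7 to 8% at 0.5 and -0.2, and higher than the central case if the correlations are stronger. There is no inflation if age is unrelated either to duration or to the structural measure.

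Three stronger readings are not supported:

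- A reader might infer that ageing will be reported as an effect of illness. In the central case most studies (75 to 82%) would show no significant result, so this is a raised risk and not a certainty.
- A reader might infer that the result would colour conclusions about who responds to levetiracetam. Section 11 contains no responder analysis and none linking structure to response.
- A reader might infer that sex and head size are confounders as well. Nothing shows that either is related to illness duration, and adjusting for age alone restored the error rate in the simulations.

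**What to change.** In section 11.2.d, replace the correlation analysis for illness duration with a partial correlation or a regression of each structural measure on duration, adjusted for age. Sex and intracranial volume may be added for precision but are optional; each uses a degree of freedom in a sample of 20 to 30. Report the age-duration correlation in the patients analysed, so that readers can see how far the two can be separated, and give the unadjusted correlation as descriptive only.

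The change needs only SAP wording, since age is already held from eligibility screening. The statistical cost is precision: the standard error is about 1.7 times larger at an age-duration correlation of 0.8, and more above that. The SAP should say in advance that if age and duration are nearly collinear, the result will be reported as unable to separate them.
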